Screening: Once the patient signs the consent form, a screening period of up to two weeks will initiate to determine the patient's eligibility for the study, prior to entering the randomization phase. Only eligible patients will enter the randomization phase.

Randomized Phase: Monthly infusions (of either B or P) will start at week 0 and continue every four weeks until week 36 (10 months) for the “randomized” phase of the study. In addition, there will be a “loading dose” at week 2 (per drug [IND] specifications). The loading dose will consist of either Belimumab or Placebo (saline) in the B or P treatment arms, respectively.

Open Label Phase: Monthly infusions (of B) will start at week 40 and continue every four weeks until week 64 (6 months) for the “open-label” phase of the study.

A comprehensive evaluation of the patient (Physical exam and history, vital signs, AEs, CBC and metabolic panel, GGT, myoglobin, pregnancy test, urinalysis, ESR, CRP, CPK, immunoglobulins, muscle and health evaluations, physician global assessment, patient self-assessments, serum level sampling) will be conducted at weeks 0, 8, 16, 24, 32, 39-40, 52, 64. A less comprehensive set of evaluations (vital signs, AEs, CBC and metabolic panel, GGT, pregnancy test) will be conducted at weeks 2, 4, 12, 20, 28, 36, 40, 44, 48, 56, 60. A detailed schedule of visits and procedures is outlined in appendix A.

A telephone follow-up conversation will also be conducted at weeks 72 and 84.

Optional Exploratory Studies

Blood based biomarker assessments and blood based RNA assessments will be performed on stored samples for consenting patients at Northwell Health only. See Appendix A (schedule of events).

b. Randomization:

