The Biostatistics Randomization Management System (BRMS) is a secure, HIPAA-compliant, web-based application that allows investigators to randomize subjects into randomized clinical trials (RCTs) using their personal computer. The BRMS allows for multi-center, stratified, and single/double blinded RCTs, using permuted blocks. Randomization notifications are automatically sent to the PI and other authorized personnel. Using BRMS is a good way to maintain compliance in RCTs.

Statistical Considerations

SPECIFIC STATISTICAL AIMS

The primary objective of the study is to compare subjects in the Belimumab group and subjects in the placebo group with respect to response (improvement) at week 40.

The specific aims of the study are to compare the two treatment arms (Belimumab vs. Placebo [P vs. B]), during the 40-week randomized phase of the study, with respect to the following:

1. Response at week 40.
2. Flare rates during the 40-week treatment period.
3. Time-to-achieve (initial) improvement during the 40-week randomized phase of the study
4. Duration of improvement during the 40-week randomized phase of the study, among those who achieved improvement (this is essentially a time-to-flare/relapse analysis from the time that you achieved improvement)
5. Change in muscle enzyme levels (CPK, myoglobin) from baseline to week 40
6. Change in MMT-8 from baseline to week 40
7. Change in prednisone dose from baseline to week 40

8. Proportion of subjects able to reduce prednisone dose to ≤ 5 mg at week 40
9. Change in B cell populations, immunoglobulin levels and BLys levels from baseline to week 40.
10. Change in autoantibody titers from baseline to week 40.
11. Rates of SAEs and AEs experienced

STATISTICAL METHODS

All subjects will be analyzed according to the intention-to-treat [ITT] principle. A subject will be considered evaluable and will be included in the intention-to-treat analysis if he/she received at least the first five of the planned infusions during the randomized phase of the study. Subjects who do not get the first five infusions will be considered ‘drop-outs’. It should be noted that the study protocol calls for patients remaining on their treatment assignment. However, adjustments in dosages of medications used in their ‘standard care’ are permitted during the first 8 weeks. Analyses that take into account the actual treatment received (e.g. accounting for compliance, etc.) will be carried out as a secondary analysis (per protocol [PP] analysis).

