
1. For specific aim 1, the two treatment arms [B vs. P] will be compared with respect to the proportion of subjects who respond to treatment at 40 weeks (improvement according to definition), using either a chi-square test or Fisher’s exact test, as appropriate.
2. For specific aim 2, either a chi-square test or Fisher’s exact test, as appropriate, will be conducted to compare the proportion of subjects who had any flares during the 40-week randomized phase. For this analysis, each subject will be categorized at the end of 40 weeks as having had one or more flares or not having had any flares. In addition, we can also examine the total number of days that a subject had a specific flare during the course of the 40-week treatment, and compare the two treatment arms using the ‘Incidence density ratio’ method.
3. For specific aim 3, standard methods for survival analysis will be carried out. The Kaplan-Meier (KM) product limit method will be used to estimate overall “time-to-achieve (initial) response/improvement”. Ninety-five percent confidence intervals will be calculated using Greenwood’s formula for computing the standard error. Subjects who have not achieved improvement as of week 40 will be considered ‘censored’ for the event (event=improvement/response).
4. For specific aim 4, similar methods as indicated for specific aim 3 will be conducted. The analysis for this aim will be limited to the subset of subjects in each treatment arm who show improvement at anytime during the randomized phase of the trial. A subject who has not flared/worsened/relapsed as of week 40 will be considered ‘censored’ for the event (event=flare/relapse).
5. For specific aims 5, 6, 7, 9 and 10, each of the outcome variables of interest (uncensored continuous or categorical) will be analyzed separately, using a mixed model approach to repeated measures analysis of variance (MMRMANOVA) with the main effects of treatment arm (B vs. P), Disease type (PM vs DM), Disease Severity (Severe vs. Less Severe) and time (baseline vs. 40 weeks). If feasible, statistical interactions between

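### The flare comparison has no rule for evaluable patients who leave before week 40, and as written they count in effect as flare-free

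*Combined protocol and SAP*

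**What the plan says.** Statistical Considerations, STATISTICAL METHODS, item 2 sets a chi-square or Fisher's exact test to "compare the proportion of subjects who had any flares during the 40-week randomized phase". For this, "each subject will be categorized at the end of 40 weeks as having had one or more flares or not having had any flares". The item has no third category, no censoring and no imputation.

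The opening paragraph of STATISTICAL METHODS defines who is analysed. A subject is "included in the intention-to-treat analysis if he/she received at least the first five of the planned infusions". "Subjects who do not get the first five infusions will be considered" drop-outs and fall outside the analysis set. Under Study Procedures and Schedule, "Monthly infusions (of either B or P) will start at week 0 and continue every four weeks until week 36", with an extra loading infusion at week 2.

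Item 2 also offers an option: "we can also examine the total number of days that a subject had a specific flare", to be compared by an incidence density ratio. No person-time denominator is given. The end of STATISTICAL METHODS adds logistic and Cox models for the listed outcomes if they prove feasible, and warns that sample size may limit them. Kaplan-Meier estimation with censoring is specified for aims 3 and 4 only. Aim 4 concerns time to flare, but only among patients who have improved.

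**The concern.** A two-way classification at a fixed time is sound when everyone is observed to that time. Here a patient enters the analysis at week 12 and may be unobserved for up to 28 of the 40 weeks. If such a patient leaves with no flare on record, the only available category is no flare, although nobody knows what happened afterwards.

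Incomplete follow-up therefore pulls each arm's flare proportion down. If more placebo patients leave, placebo looks better than it is and a real benefit shrinks. If more belimumab patients leave, a benefit can be exaggerated or created. Even equal leaving narrows a true difference. Incidence of flares heads the list of secondary endpoints, and the choice to keep a failing patient in the study is left to the physician and principal investigator, so complete follow-up cannot be assumed.

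**Working it through.** **The plan's own figure.** No flare rate, dropout rate or flare power is stated. The only sample-size figure concerns response at week 40: 5% v 50%, two-sided alpha 0.05, 80% power, no dropout. With pooled variance, n = [1.960 × √(2 × 0.275 × 0.725) + 0.842 × √(0.05 × 0.95 + 0.50 × 0.50)]² / 0.45² = 14.2, so 15 per arm. This matches the plan but says nothing about flares.

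**When a patient becomes evaluable.** Infusions fall at weeks 0, 2, 4, 8 and 12, so the fifth is at week 12. Unobserved time can reach 40 − 12 = 28 weeks.

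**Size of the distortion.** Every rate below is an assumption. F is the true 40-week flare risk and d the probability of leaving during weeks 12-40, independent of flare. With constant hazards:

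- λ = −ln(1 − F)/40 and μ = −ln(1 − d)/28
- counted proportion = 1 − e^(−12λ) + e^(−12λ) × λ/(λ + μ) × [1 − e^(−28(λ + μ))]

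Example, F = 60% and d = 30%: λ = 0.02291, μ = 0.01274, e^(−12λ) = 0.7597. Counted = 0.2403 + 0.7597 × 0.6426 × 0.6314 = 54.9%.

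| True risk, placebo / belimumab | Leaving, placebo / belimumab | Counted, placebo / belimumab | True difference | Counted difference | Distortion |
|---|---|---|---|---|---|
| 60% / 30% | 30% / 10% | 54.9% / 29.0% | 30 | 25.8 | −4.2 |
| 60% / 30% | 40% / 10% | 53.0% / 29.0% | 30 | 23.9 | −6.1 |
| 50% / 50% | 30% / 10% | 45.4% / 48.5% | 0 | −3.1 | −3.1 |
| 50% / 50% | 40% / 10% | 43.7% / 48.5% | 0 | −4.8 | −4.8 |

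Differences are placebo minus belimumab, in percentage points, taken before rounding. Swapping the leaving rates between arms in the 50% / 50% rows reverses the sign.

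**Sensitivity to when patients leave.**

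- Uniform over weeks 12-40: counted = (1 − d) × F + d × (mean of F(t) over weeks 12-40). For F = 50% the mean is 35.6%, so 30% v 10% leaving gives 45.7% v 48.6%, a false difference of 2.9 points. For 60% v 30% true risk with the same leaving, the difference is 26.1. With 20% leaving in both arms it is 28.7.
- Everyone leaving at week 12: counted = (1 − d) × F + d × F(12). For F = 50%, F(12) = 18.8%. Leaving of 30-40% v 10% gives 40.6-37.5% v 46.9%, a false 6.2 to 9.4 points. For 60% v 30% true risk it gives 49.2-45.6% v 28.0%, so the difference falls to 21.2-17.6. This is the extreme timing.

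**What it means at 15 per arm.** In the 60% scenario the expected placebo loss is 15 × (60 − 54.9)/100 = 0.8 flares to 15 × (60 − 53.0)/100 = 1.05 flares, about one patient. As an example, 10 v 3 flares gives Fisher p = 0.025, and 9 v 3 gives p = 0.060. Losing three placebo flares (7 v 3) gives p = 0.245, but that is more than this model predicts and would need leaving linked to worsening.

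**What censoring would do.** Under the same independent-leaving assumption, a Kaplan-Meier estimate censored at leaving targets the true 40-week risks.

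**The case against.** The strongest reply is that the plan never says leavers count as flare-free. It is silent, and the team could treat them as missing or as flared. That is correct, and a reader should not infer a written rule. But the text places each subject in one of two groups and offers nothing else, so the flare-free count is what following it produces.

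A reader might also infer that all early leavers are scored flare-free. The documents do not support that: those without five infusions are removed from the analysis. That exclusion after randomisation is a separate problem.

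Nor do the documents show that the incidence density ratio is computed wrongly. Neither numerator nor denominator is defined; only "the total number of days that a subject had a specific flare during the course of the 40-week treatment" is mentioned. Days in flare measure duration, so the description does not supply the missing time at risk. The Cox model could, but it depends on feasibility. Aim 4 compares only improvers, which is not a comparison of the randomised groups.

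Some mitigation is real. A new start or increase of treatment for myositis after week 8 is itself a flare, so worsening that is treated before a patient leaves is captured, and treatment failures may stay in the study. The size is also modest: one patient in 15 is 6.7 points, and the standard error of a difference at 50% is √(2 × 0.25/15) = 18 points. Flare is unpowered, and its place at the head of the list gives it no stated priority.

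These arguments limit the weight of the point. They do not supply the rule.

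**Conclusion.** The concern holds as a gap in the analysis of aim 2: evaluable patients who leave between weeks 12 and 40 without a recorded flare are in effect counted as flare-free. Under assumed leaving of 30-40% v 10%, spread over that period and unrelated to flare risk, the comparison moves by about 3 to 6 points. It moves more if leaving is concentrated near week 12 or if patients leave as they worsen. Worsening on the core set measures is assessed only about every 8 weeks, so a patient can deteriorate and leave between visits with nothing recorded.

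A reader might infer a large bias in a known direction. The documents do not support that, because they give neither flare nor dropout rates, and the direction depends on which arm loses more patients. The change is worth making because the plan already uses the better method for aims 3 and 4.

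**What to change.** Make time from randomisation to first flare the between-arm analysis for aim 2:

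- Include all randomised patients with any follow-up, not only those with five infusions.
- Report the Kaplan-Meier 40-week flare probability by arm, with a log-rank test, censoring at the last flare assessment.
- Leave the log-rank test unstratified, or stratify by one factor only. Disease type by severity gives four strata, too sparse for 30 patients.
- If a rate is wanted, use the number of flares per person-time at risk in place of flare-days.
- Keep the week-40 proportion as supportive, with a stated rule for leavers.
- Add one sensitivity analysis that counts leavers as flared.

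The cost is wording in the analysis plan; no visit or procedure changes. There are two downsides. Censoring assumes that leaving is unrelated to flare risk, which is doubtful if patients leave as they worsen, hence the sensitivity analysis. Flares found through the core set measures are timed only to visits about 8 weeks apart, so event times are approximate.

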2. Elevation of at least one muscle enzyme (creatinine kinase [CK]; myoglobin; alanine aminotransferase [ALT]; or aspartate aminotransferase [AST]) to a minimum level of 1.3 times the upper limit of normal.
3. Physician Global Assessment ≥ 2.0 cm using a visual analogue scale (VAS) 10.0 cm in length.
4. Patient Global Assessment ≥ 2.0 cm using a visual analogue scale (VAS) 10.0 cm in length.
5. Global extra muscular disease activity score ≥ 1.0 cm using a visual analogue scale (VAS) 10.0 cm in length. This score is based on the investigator's composite assessment of disease activity of the constitutional, cutaneous, skeletal, gastrointestinal, pulmonary and cardiac scales on the Myositis Disease Activity Assessment Tool (MDAAT).
6. HAQ disability index with a minimum value of 0.25.

The patient will be required to meet an MMT 8 score of $\leq 125/150$ as a major CSM criterion and at least 2 other CSM criteria to classify as an active disease.

In addition, for patients with ≥ 7 years of IIM, muscle biopsy or muscle MRI within 4 months prior to enrollment will be required to document active myositis to avoid enrolling patients with

significant index of damage/ muscle atrophy. This is not applicable to DM patients with a cutaneous VAS score of >3 cm on a 10 cm VAS scale (MDAAT).

Response rate: The response rate will be assessed by the percentage of patients meeting the definition of improvement (DOI). DOI is based on the definition of improvement developed by the International Myositis Assessment and Clinical Studies Group utilizing 6 core set measures.

DOI: DOI is defined as $\geq 20\%$ improvement in any 3 of the CSM, with no more than 2 CSM worsening by $\geq 25\%$ (excluding MMT)¹¹.

Definition of Worsening (DOW): Determination of worsening of the disease activity will be based on the definition of worsening (DOW) criteria developed by the International Myositis Assessment and Clinical Studies Group (IMACS) utilizing 6 core set measures¹¹:

1. worsening of Manual Muscle testing by $\geq 20\%$ and or Physician Global worsening of ≥ 2 cm on a 10 cm VAS or
2. Global extra muscular organ disease activity worsening by ≥ 2 cm on a 10 cm VAS on MDDAT, or
3. 3 of 6 CSM worse by $\geq 30\%$

Disease Flare: IIM Disease Flare is recorded when the patient:

1. reaches DOW;
2. new start or dose increase of corticosteroid or immunosuppressive agent for treatment of IIM after study week 8;

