There will be no formal interim analyses or formal statistical stopping rules. However, statistical summaries of adverse event rates using 95% exact confidence intervals will be provided to the data safety monitoring board as need. During regular bi-annual meetings the data safety monitoring board will evaluate the overall rate of adverse events and unanticipated problems. Upon review the group will determine whether there are any changes needed to the anticipated benefit-to-risk assessment and if the study should continue. The results of these regular meetings will be recorded and disseminated to the other participating clinical sites. Safety data will be collected in the form of adverse events (AEs), serious AEs (SAEs) and laboratory parameters (e.g., hematology, chemistry, etc.). AEs will be recorded with the date of onset, severity, relationship to study drug, and disposition. AEs will be translated into a standard classification system such as COSTART or MedDRA. AE data will be summarized according to incidence rates, by treatment arm and by whether or not the AE was treatment related. AEs will be summarized using descriptive statistics and tabulated according to treatment group for each strata. The AE report will be descriptive, rather than inferential.

SAMPLE SIZE CONSIDERATIONS

We plan to enroll 30 evaluable patients with 15 in each of two treatment arms [B vs. P].

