From available trials in IIM, there is an observed placebo effect of 0%-40% at 12 weeks^{9,10} and 0% at 52 weeks⁹. These results demonstrate that the placebo response rate at 40 weeks can be very variable. One clinical study looking at rituximab in myositis was the first prospective, double-blind, randomized trial in myositis and the largest clinical trial ever performed in the inflammatory myopathies¹⁶. This trial employed a unique design; subjects were divided into two groups: early-start and delayed-start of rituximab. Overall, 83% of enrolled subjects (with severe refractory disease) met the DOI by the end of the trial, despite lack of statistical significance between groups. An alternate double-blind, placebo-controlled trial of etanercept (50 mg subcutaneously weekly for 52 weeks) where 16 subjects were randomized showed that: all 5 subjects receiving placebo were treatment failures (median time to treatment failure: 148 days)¹⁷. In contrast, 5 of 11 subjects in the etanercept arm were successfully weaned off prednisone; the median time to treatment failure in this group was 358 days ($p = 0.0002$). This data shows that for myositis trials, placebo response is often close to 0%. In order to achieve a clinically meaningful difference between study treatment arms, the response rate of the treatment group would need to be at least 50%.

We hypothesize (optimistically) the response rate at 40 weeks in the placebo arm to be 5%. We further assume that a magnitude of difference of 45% would be clinically meaningful (this corresponds to a 50% response rate in the Belimumab arm).

Based on the assumption that a difference of 45% in response rates at 40 weeks between Placebo and the investigational agent, Belimumab, would be clinically meaningful, then, a two group chi-square test ($\alpha=0.05$, two sided test) will yield 80% power to detect a difference between the Placebo arm week 40 response rate of 5% and a Belimumab-treated arm week 40 response rate of 50% (Odds ratio=19) when the sample size in each group is 15, assuming the dropout rate is 0%.

Table 1 below shows the sample size requirements for various pairs of (hypothesized) 40-week response rates and assumptions on what would be a clinically meaningful difference between treatment arms. Corresponding sample sizes are provided for the specified range of parameters. Calculations were based on a two-sided chi-square test to achieve 80% power ($\alpha=0.05$).

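### The optional flare-day analysis pairs days in flare with an event-rate method, with no variance stated and no rule for when a flare ends; the usual variance would badly inflate false positives

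*Combined protocol and SAP*

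**What the plan says.** Incidence of flares over the 40-week randomized phase is the first secondary endpoint listed under Endpoints and is specific aim 2 under Statistical Considerations.

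Item 2 of STATISTICAL METHODS gives two analyses. The committed one is a chi-square or Fisher's exact test for which "each subject will be categorized at the end of 40 weeks as having had one or more flares or not having had any flares". The second is optional: "we can also examine the total number of days that a subject had a specific flare during the course of the 40-week treatment", and then "compare the two treatment arms using the ‘Incidence density ratio’ method". No standard error, interval, overdispersion term or patient-level test is given for this second comparison. The later sentence on logistic and Cox models does not supply one.

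Under Definitions, "Disease Flare: IIM Disease Flare is recorded when the patient" meets one of three triggers: the worsening criteria, a new or increased corticosteroid or immunosuppressive after week 8, or an early steroid increase not brought back near baseline by week 12. All three say when a flare is recorded; none says when it is over. On size, the plan says "We plan to enroll 30 evaluable patients with 15 in each of two treatment arms".

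**The concern.** An incidence density is the number of new events divided by the person-time at risk of a new event. The usual standard error of a ratio of two such densities takes each numerator as a Poisson count, so information grows with every unit counted. If the units are days in flare, one patient with a four-week flare contributes 28 events. Those days all come from one onset, and during them the patient is not at risk of a further onset. The independent information is at most one observation per patient, 15 per arm.

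At stake is a secondary efficacy claim. With 15 per arm the any-flare test has little power. A flare-day ratio with a falsely small p-value, for benefit or for harm, could sit beside a clearly null any-flare result from the same patients, and the report would have to choose between them.

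**Working it through.** **Inputs from the documents.** 15 patients per arm, 1:1; randomized phase of 40 weeks = 280 days; no dropout in the sample size section; core set measures every 8 weeks in the randomized phase.

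**Inputs that are assumptions.** The share of patients who flare and how long a flare lasts. The main range is 30% to 50% flaring, with one flare of fixed length per flaring patient and equal follow-up. The nominal level is taken as two-sided 5%, as for the primary test; none is stated for flares.

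**Plan's own figure.** The documents give none for the flare-day comparison. The 15 per arm, for 5% versus 50% response, reproduces: n = [1.96·√(2 × 0.275 × 0.725) + 0.842·√(0.05 × 0.95 + 0.5 × 0.5)]² / 0.45² = 2.88 / 0.2025 = 14.2, rounded up to 15.

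**Standard test on flare days.** Let x and y patients flare in the two arms, each for d days. The totals are A = xd and B = yd over equal person-time.

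- Poisson SE of the log ratio = √(1/A + 1/B).
- Equivalent score form: z = |A − B| / √(A + B) = |x − y|·√d / √(x + y).

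The √d is the fault: z grows with flare length although the number of patients is unchanged. The test rejects when |x − y| > 1.96·√((x + y)/d). At 30% flaring, 30 × 0.3 = 9 flares are expected. With 56-day flares the threshold is then 1.96·√(9/56) = 0.79, so 5 versus 4 patients counts as significant.

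**False-positive rate with no treatment effect.** Sum Bin(x; 15, p) × Bin(y; 15, p) over all pairs (x, y) with z > 1.96. Exact enumeration agrees with simulation.

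| Flare length | 30% flaring | 50% flaring |
|---|---|---|
| 7 days | 37% | 30% |
| 14 days | 55% | 47% |
| 28 days | 66% | 59% |
| 56 days | 84% | 68% |

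**Standard error.** With 28-day flares and 30% flaring, the Poisson SE averages 0.14 and the true SD of the log ratio is 0.64 (trials with flares in both arms), so the SE is about 4.7 times too small. Across the table the factor runs from about 2.0 (7 days, 50% flaring) to 6.6 (56 days, 30% flaring).

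**Wider assumptions (simulation, 20,000 trials each, 10% to 70% flaring).** Uniform 7-day flares: 16% to 48%. Exponential durations: 65% to 71% at mean 14 days, 74% to 79% at 28, 82% to 85% at 56. If a flare were taken to last from one core-set visit to the next, its length would come in steps of about 8 × 7 = 56 days.

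**One data set, both analyses.** Take 6 versus 4 patients, each with one 28-day flare: 168 versus 112 days, ratio 1.5, z = 56/√280 = 3.35, exact p = 0.001. Fisher's test on 6/15 versus 4/15 gives p = 0.70.

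**With the patient as the unit.** A permutation test of per-patient totals (mean duration 28 days) rejects in 3.3%, 5.0% and 5.4% of null trials at 20%, 30% and 50% flaring. A per-patient Mann-Whitney test gives 4–5%. Counting each patient's flare once as the event, with the ordinary Poisson variance, gives 0.6% to 3.2%. So the inflation comes from counting days, not from the ratio method.

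**The case against.** The best defence is that the plan does not write out the faulty variance. It names a method and stops; a robust, bootstrap or permutation variance would remove the inflation. That stands. A reader might infer that the planned interval is too narrow, but no interval or standard error is stated. What can be said is that none is specified and the standard one for the named method is wrong for this quantity.

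A reader might also infer that chance differences will usually look significant. The documents do not support that, because they give no flare length. Rejection is below one half for uniform 7-day flares and, at 50% flaring, for 14-day flares. It exceeds one half at 28 days and longer, and for the variable durations examined.

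Nor do the documents show that flare days could never be obtained. The components of worsening are reassessed at weeks 8, 16, 24, 32 and 40, and prednisone dose is needed for two other secondary endpoints. A rule is missing, not all the data.

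Finally, the analysis is discretionary and supplementary. The committed any-flare test takes the patient as the unit and is valid, and nothing ties flare days to the primary endpoint, sample size or a decision rule. That limits the severity.

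One might read the sentence as flares over days at risk, which would be standard. But it makes days with a flare the quantity examined.

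**Conclusion.** The point holds as a moderate one. An optional analysis of a secondary endpoint applies an event-rate method to days in flare, specifies no variance, and rests on a quantity with no defined end. With the standard variance the nominal 5% test would reject in about 30–37% (7-day flares), 59–66% (28-day) or 68–84% (56-day) of null trials, with a standard error about 2 to 6.6 times too small. These sizes assume 15 per arm, equal follow-up, 30% to 50% of patients flaring, and one fixed-length flare each. The missing end rule is a gap whichever variance is used. The primary analysis and the any-flare comparison stand as they are.

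**What to change.** Reword the second half of item 2 before unblinding, choosing one of two forms.

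1. **Flares as events.** Use the incidence density ratio for the number of flares, or first flares, per patient-time at risk. Specify an exact conditional test on first flares or, for repeated flares, a patient-level (robust or negative binomial) variance. The exact test will be conservative at this size. The robust and negative binomial options were not checked here with 15 per arm and few flares, so simulate them before adoption.
2. **Time in flare.** Have the investigators define when a flare ends. Compute one total of flare days per patient, 0 if none, and compare arms by a permutation or Mann-Whitney test.

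In either form, state that the comparison is supplementary to the any-flare test. The first form is a change of wording only. The second also needs the end rule, and a check that the end date can be recorded or derived between 8-weekly assessments. The price in both is a wider interval than the standard formula would print, which reflects the information that 30 patients can give.
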